7.4. Follow-up Period

During the 4-week follow-up period, the continued safety of the subjects after discontinuation of study drug will be assessed.

7.4.1. Visit F1 (Day 141; Week 21; Follow-up Visit)

The Follow-up Visit should occur approximately 4 weeks after completion of the EoT visit.

At Visit F1/EoS, appropriate study site personnel should:

- Record AEs and update medications.
- Review the subject's eDiary entries.
- Confirm that the subject has recorded the date and time of their last doses of glucocorticoid and mineralocorticoid (if applicable) prior to the visit using the eDiary. If not, ask the subject to record the information.
- If the subject is a premenopausal woman, confirm that she has recorded the start date of her last menstrual period using the eDiary. If not, ask the subject to record the information.

- Record vital signs and weight.
- Perform a brief PE, with particular attention to assessing the subject for adrenal insufficiency.
- Within 30 minutes prior to administration of morning replacement glucocorticoid and mineralocorticoid (if applicable) doses, collect blood samples for hematology, chemistry, and hormones (17-OHP, P, cortisol, A4, ACTH, total testosterone, and 11-ketotestosterone).
 - For each study visit, the first hormone sample collection that is obtained at the study site should be done between 6-10 AM (06:00-10:00), as close to 8 AM (08:00) as practicable.
 - Hormones should not be collected if the subject already took their replacement glucocorticoid and/or mineralocorticoid dose that morning; instead, the sample collection should be rescheduled for the next day or as soon as is feasible.
- For female subjects of childbearing potential only, collect a urine sample and perform a urine pregnancy test.
- Ask the subject to self-administer their morning replacement glucocorticoid and mineralocorticoid (if applicable) doses.
- Ask the subject to record the time of glucocorticoid and mineralocorticoid (if applicable) administration using the eDiary.
- Collect any provisioned devices.
- Once all Visit F1 procedures have been completed, discharge the subject from the study.

7.5. Early Termination (ET)

Enrolled subjects who withdraw from the study prior to the EoT visit should return to the study site for an ET visit, which consists of the same procedures as at EoT. Any provisioned devices should also be collected.

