4.4. Subject Withdrawal Criteria

In accordance with the Declaration of Helsinki and subsequent conferences, subjects have the right to withdraw from the study at any time for any reason. The Investigator and the Sponsor also have the right to withdraw subjects from the study. Subjects may be removed from the study for the following reasons:

1. In the Investigator's judgment, it is in the best interest of the subject to discontinue study participation.
2. The subject experiences an AE that would preclude further treatment with the study drug.
3. The subject withdraws consent for continued participation or refuses further treatment with the investigational product.
4. The subject is noncompliant with the protocol.

Enrolled subjects who withdraw from the study prior to the T5/End-of-Treatment (EoT) visit should return to the study site for an Early Termination (ET) visit, which consists of the same procedures as at T5/EoT. The reason for and date of withdrawal/removal from the study must be documented in the subject's medical records. Investigational site personnel must attempt to determine whether the reason for withdrawal was an AE and if so, this must be reported in accordance with the procedures provided in [Section 6.10](#). For all subjects who do not complete the study, regardless of the duration of treatment, all relevant information related to the withdrawal/removal will be entered into the electronic case report form (eCRF).

Subjects who withdraw or are removed from the clinical study after enrollment will not be replaced. All enrolled subjects will be fully accounted for and documented in the final clinical study report (CSR).

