5.3.1. Timing and Administrative Dosing Conditions

Study drug should be taken approximately 12 hours apart (twice per day dosing). The time of day that the dose is taken should be as consistent as possible (e.g., every morning at 8 AM (08:00) and every evening at 8 PM (20:00)). Using the eDiary, subjects should record the actual time of their doses of study drug (if applicable), glucocorticoid, and mineralocorticoid (if applicable), particularly those taken on the day prior to and the day of study visits. On the morning of study visits, including at Visit T5/EoT, subjects should wait to take their morning doses of study drug (if applicable), glucocorticoid, and mineralocorticoid (if applicable) until directed by personnel at the study site.

Study drug should be taken with a non-alcoholic beverage (except grapefruit juice) immediately after consumption of food. No specific food contents are required and subjects should maintain usual eating practices. If a full meal is not possible or not aligned with a subject’s usual eating practices, a light snack should be consumed prior to taking study drug.

The first dose of each dose level will be administered at the site with food. See the Pharmacy Manual for more details.

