6.10.5. Pregnancy Reporting

Any pregnancy that occurs following study drug dosing where the estimated date of conception occurred either prior to the study termination visit or within 30 days of last study treatment must be reported. The Investigator should report the pregnancy using the Pregnancy Form within the EDC system within 24 hours of being notified. Via the EDC system, Clinical Safety will receive the report in parallel via email at [contact]. **The contact information for reporting pregnancies is the same as for reporting SAEs (Section 6.10.4.2).**

A subject becoming pregnant while on study drug will immediately be withdrawn from the study and early termination (ET) study procedures will be performed.

The subject should be followed by the Investigator until completion of the pregnancy. If the pregnancy ends for any reason before the anticipated date, the Investigator should notify Clinical Safety as specified in the Safety Manual. At the completion of the pregnancy, the Investigator will document the outcome of the pregnancy. If the fetus has a congenital anomaly, the Investigator should follow the procedures for reporting an SAE.

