7.3.9. Visit T5 (Day 113; Week 17; End-of-Treatment)

At Visit T5, appropriate study site personnel should:

- Record AEs and update medications.
- Review the subject's eDiary entries and reinforce instruction on the use of the eDiary as needed.
- Confirm that the subject has recorded the date and time of their last doses of glucocorticoid, mineralocorticoid (if applicable), and study drug prior to the visit using the eDiary. If not, ask the subject to record the information.
- If the subject is a premenopausal woman, confirm that she has recorded the start date of her last menstrual period using the eDiary. If not, ask her to record the information.
- Record vital signs and weight.
- Perform a complete PE.
- Obtain a 12-lead ECG.
- Within 30 minutes prior to administration of study drug and morning replacement glucocorticoid and mineralocorticoid (if applicable) doses, collect blood samples for hematology, chemistry, PT, aPTT, INR, hormones (17-OHP, P, cortisol, A4, ACTH, total testosterone, and 11-ketotestosterone), PK, and a serum storage sample; and collect a saliva sample for 17-OHP, P, and cortisol.
 - For each study visit, the first hormone sample collection that is obtained at the study site should be done between 6-10 AM (06:00-10:00), as close to 8 AM (08:00) as practicable.
 - Hormones should not be collected if the subject already took their replacement glucocorticoid and/or mineralocorticoid dose that morning; instead, the sample collection should be rescheduled for the next day or as soon as is feasible (the subject should also continue taking study drug BID until the Visit T5 hormone samples are collected).
- Collect a urine sample for urinalysis.

- For female subjects of childbearing potential only, collect a urine sample and perform a urine pregnancy test.
- If the subject does not have sufficient remaining study drug to administer a single dose, or did not bring their study drug to the study visit, dispense study drug.
- Ask the subject to self-administer study drug with food and a nonalcoholic beverage (excluding grapefruit juice) while at the study site.
- Ask the subject to self-administer their morning replacement glucocorticoid and mineralocorticoid (if applicable) doses.
- Ask the subject to record the time of study drug, glucocorticoid, and mineralocorticoid (if applicable) administration using the eDiary.
- Collect study drug and assess compliance.

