- ^a Study procedures and visits during the Treatment Period have a window of ± 2 days. Study procedures and visits during the Screening, Baseline, and Follow-up Periods have a window of ± 7 days. Only Cohort 2 subjects should undergo Visit S2; Cohort 1 subjects should skip Visit S2 and proceed to the Baseline Visit (Visit B1). Subjects who discontinue the study during the Treatment Period prior to Visit T5/EoT should undergo an ET visit, which consists of the same procedures as Visit T5/EoT. Please note that the assigned Study Day is the first day of the corresponding Study Week. Additionally, target study days shown for Screening and Baseline are for a hypothetical Cohort 2 subject who requires 1 GC dose down-titration during Screening and none during Baseline, and has 17-OHP checked 2 weeks after GC dose down-titration; however, regardless of the assigned Study Day/Week, with agreement of the Medical Monitor, the duration of the Screening and Baseline Periods may be adjusted based on the needs of the individual subject.
- ^b Subjects should note the actual time of their doses of study drug (if applicable), GC, and MC (if applicable), particularly those taken on the day prior to and the day of study visits. On the morning of study visits, subjects should wait to take their morning doses of study drug (if applicable) and GC and MC (if applicable) replacement until directed by personnel at the study site. On the morning of Visit T5, subjects who do not have sufficient remaining study drug to administer a single dose may be dispensed study drug if needed.
- ^c Height will be assessed at Visit S1 only.
- ^d A complete PE will be performed at Visits S1, T1, and T5/EoT. A brief PE will be performed at Visits T2, T3, T4 and F1/EoS.

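### The Early Termination visit repeats the end-of-treatment procedures, on-site dose included, with no exception for subjects withdrawn for an adverse event or pregnancy

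*Protocol*

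**What the plan says.** The Early Termination (ET) visit is defined by cross-reference in three places: Protocol Section 4.4; Section 7.5, where subjects who withdraw before EoT "should return to the study site for an ET visit, which consists of the same procedures as at EoT"; and Table 6 footnote a in Appendix 1, where subjects who discontinue early "should undergo an ET visit, which consists of the same procedures as Visit T5/EoT". Section 7.5 adds only the return of provisioned devices.

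The list referred to is Section 7.3.9 (Visit T5). After the assessments, the 0-hour samples and the urine pregnancy test, it covers a subject who has too little drug left or "did not bring their study drug to the study visit, dispense study drug". The next bullet reads: "Ask the subject to self-administer study drug with food and a nonalcoholic beverage (excluding grapefruit juice) while at the study site". Plasma PK and serum 17-OHP are then drawn at 1, 2, 3 and 4 hours, and saliva at 2 and 4 hours, all timed from the study drug dose. If the 0-hour hormone samples have to be rescheduled because the morning steroid was already taken, the subject is to stay on twice-daily study drug until they are collected.

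Three kinds of subject reach this visit with treatment already ruled out. Section 4.4 lists as withdrawal reasons "The subject experiences an AE that would preclude further treatment with the study drug", and a subject who "refuses further treatment with the investigational product". Section 6.10.5 states: "A subject becoming pregnant while on study drug will immediately be withdrawn from the study and early termination (ET) study procedures will be performed".

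**The concern.** A site that follows the cross-reference as written gives study drug, dispensing it first if necessary, to a subject who was withdrawn because an adverse event ruled out further treatment or because she is pregnant. For pregnancy the wording is firmer than elsewhere: ET procedures will be performed, not should be. The protocol itself treats exposure around pregnancy as a risk. It requires two contraceptive methods until 30 days after the last dose (Section 4.2, item 8) and immediate withdrawal on pregnancy.

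What is at stake is subject safety in a small number of cases, and a protocol in which the safe action departs from the listed procedures. The analysis of the trial is not at stake.

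**Working it through.** The plan states no figure on this point, so the main check is a trace through the text. The arithmetic only sizes the exposure and the cost of the fix.

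**Step 1: route and content.** Section 4.4 (adverse event) and Section 6.10.5 (pregnancy) lead to ET. ET equals the T5 list (Sections 4.4 and 7.5, Table 6 footnote a). The T5 list includes dispensing if needed, an on-site dose, and continued dosing if sampling is rescheduled (Section 7.3.9). Within that list, mineralocorticoid dosing is qualified by 'if applicable' and the pregnancy test is limited to women of childbearing potential. The study drug bullet carries no qualifier.

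**Step 2: search for an exemption.**

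| Place | What it provides | Does it withhold drug at ET? |
|---|---|---|
| 5.3.1 and opening of 7 | On visit mornings, study drug (where applicable) waits until the site directs it | No. It also covers visits without drug, and it names T5/EoT as a visit where the subject waits for the dose |
| 5.3.3 | Dose may be reduced or paused for safety at any time, whatever the visit schedule | No. General permission; the ET list is unchanged |
| 10.3 | Subject may stop study drug at any time without penalty | Covers refusal; silent on adverse event and pregnancy |
| Table 6 footnote b | Dispensing at T5 is optional | No. The dosing bullet stands |
| 6.11 and Table 6 footnotes e, f | Sample times may refer to steroid and/or study drug doses | No. Sample timing only |

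Express exemptions found: none.

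**Step 3: exposure per affected subject.** Table 2 gives 1 to 4 tablets of 500 mg per dose: 1 × 500 = 500 mg to 4 × 500 = 2000 mg, taken once on site. If sampling is rescheduled, each day of delay adds up to two doses: 2 × 500 = 1000 mg to 2 × 2000 = 4000 mg per day.

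**Step 4: samples lost if the dose is omitted.** Per ET visit there are 4 PK, 4 serum 17-OHP and 2 saliva postdose samples. Planned postdose PK samples lie between two extremes:

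- all subjects under amendment 1 (visits T1 to T4, SAP Table 1): 4 × 4 × 20 = 320
- all subjects under amendment 2 (visits T1 to T5, SAP Table 2): 4 × 5 × 24 = 480

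The loss per affected subject is 4/480 = 0.83% to 4/320 = 1.25%. Serum 17-OHP has the same counts. Saliva gives 2/240 = 0.83% to 2/160 = 1.25%. The documents give no withdrawal rate. If 1 to 3 subjects were affected (an assumption), the PK loss would be 4 to 12 samples, from 4/480 = 0.83% to 12/320 = 3.75%. The 20 to 24 are planned evaluable subjects; with more enrolled, the shares are smaller.

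**Step 5: primary endpoint.** SAP Sections 6.2 and 7.5 classify response on predose serum 17-OHP. Whether a dose follows the 0-hour sample does not alter that value.

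**The case against.** The best reply is that the protocol, read as a whole, already deals with this. An adverse event that precludes treatment is a finding about that subject, whereas the ET cross-reference is generic and worded as should. Section 5.3.3 allows a safety hold regardless of the visit schedule. Section 5.3.1 says, "including at Visit T5/EoT, subjects should wait to take their morning doses of study drug (if applicable", with the qualifier attached to the drug, and the matching text at the start of Section 7 governs every study visit, ET included. Section 10.17 permits departures without prior approval to remove an immediate hazard. No sensible investigator would dose these subjects.

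Much of this stands, and it is why the point is small. It shows that a site may withhold the drug, but not that the protocol tells it to. Section 10.9 has missed procedures documented as deviations, so withholding would have to be recorded or justified case by case. For pregnancy, the generic 'should' is replaced by a direct instruction.

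The reply succeeds fully on refusal. A reader might infer that subjects who refuse treatment are also put at risk. The documents do not support that: the T5 list only asks the subject to take the drug, and Section 10.3 lets the subject decline. For them the request is inappropriate but raises no safety concern.

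**Conclusion.** The gap is real. It is a low-frequency drafting error with a safety aspect, confined to subjects withdrawn for a treatment-precluding adverse event or for pregnancy, and it is worth correcting. The size is one dose of 500 to 2000 mg per affected subject, plus up to two doses per day if hormone sampling is rescheduled. How many subjects would be affected cannot be derived from the documents.

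Three wider readings should be resisted:

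- The trial's efficacy result is not put in doubt, because response is judged on predose 17-OHP.
- The concern does not extend to every early terminator. Those still on drug, for whom treatment is not precluded, can follow the list as it stands.
- Adding single doses across different subjects into a total in milligrams describes nobody's risk.

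The conclusion assumes only that a site might apply the cross-reference literally. Most investigators probably would not.

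**What to change.** Add to Sections 7.5 and 6.10.5 and to Table 6 footnote a, with a cross-reference from Section 4.4:

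> At the ET visit, study drug is not dispensed, administered or continued if it has been stopped or if the subject is withdrawn for an AE or pregnancy. In that case the postdose PK, serum 17-OHP and saliva samples are omitted. All safety assessments, the 0-hour hormone and PK samples, the pregnancy test and drug return are kept, and the time of the last study drug dose is recorded.

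The word 'continued' is needed because of the rescheduling instruction in Section 7.3.9. The condition that drug has been stopped also covers subjects who have stopped because they refuse treatment.

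If the sponsor wants to keep the 1 to 4 hour serum 17-OHP and the 2 and 4 hour saliva samples, the statement must say that they are timed from the morning glucocorticoid dose, because Section 7.3.9 times them from study drug. Table 6 footnotes e and f and SAP Section 6.3 are compatible with that timing. The postdose PK samples cannot be rescued in this way, since Table 6 footnote k ties them to the dose.

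The cost is a minor amendment. Section 10.17 requires the IRB/EC to be informed and may require documented approval, at about 10 to 12 sites; the change can travel with the next amendment. Four postdose PK samples are lost per affected subject, and four serum 17-OHP and two saliva samples as well if these are omitted. No change to the SAP schedule footnotes is needed, because the SAP does not direct dosing at sites.

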8. QUALITY CONTROL AND ASSURANCE

Before any subjects can be consented at an investigational site and prior to the conduct of any protocol-specific procedures, formal training of investigational site personnel will be conducted. The Investigator and all relevant investigational site staff are to be trained on all aspects of the study for which they are responsible. Site personnel may be trained at a formal initiation visit, at an Investigator's Meeting, or by another means as necessary. Monitoring and auditing procedures will be conducted in compliance with the International Council on Harmonisation (ICH) Guidelines for Good Clinical Practice (GCP). Onsite verification of the eCRFs for completeness and clarity, crosschecking with source documents and clarification of administrative matters will be performed on a regular basis. Monitoring visits will occur at regular intervals as noted in the monitoring plan. Through frequent communications with the investigational site, the clinical research associate (CRA) will ensure that the investigation is conducted according to protocol design and all applicable regulatory requirements. Additional details on the monitoring of this study are provided in [Section 10.5](#). During the course of the study, investigational sites, the study database and all associated study documentation may be subject to quality assurance audits by the Sponsor, or their appointed representatives, on a planned or as-needed basis. In addition, representatives of associated regulatory bodies may conduct inspections at their discretion. The Investigator is responsible for ensuring direct access to all protocol-specific materials for the purpose of these activities.

9. STATISTICS

9.1. General Considerations

A separate Statistical Analysis Plan that includes a more technical and detailed description of the planned statistical analyses will be prepared prior to final database lock.

9.2. Sample Size

Based on results of the previous Phase 2 study of nevanimibe HCl in classic CAH (ATR-101-201), the sample size of approximately 20-24 evaluable subjects is considered to be sufficient for assessing whether nevanimibe HCl at doses of 500-2000 mg BID has clinically meaningful efficacy in the treatment of classic CAH. No formal sample size calculation was done. An evaluable subject is defined as a subject who has efficacy data following at least 8 weeks of continuous dosing with nevanimibe HCl.

9.3. Analysis Populations

Efficacy – The modified Intent-to-Treat (mITT) Population, used for all the efficacy summaries, is defined as all enrolled subjects who received at least one dose of study drug and had at least one post-baseline serum 17-OHP value.

Per Protocol – The Per Protocol (PP) Population, used for all the efficacy summaries, is defined as all enrolled subjects who received at least one dose of study drug, had at least one post-baseline serum 17-OHP value, and did not have any major protocol deviations that would compromise assessment of efficacy.

Safety – The Safety Population, used for all the safety summaries, is defined as all enrolled subjects who received at least one dose of study drug.

Pharmacokinetic – The Pharmacokinetic (PK) Population will include all subjects with measurable study drug concentrations. PK analyses will be based on the PK Population.

9.4. Disposition and Baseline Characteristics

Disposition, including reason for discontinuation from the study, will be summarized. Demographic information and subject characteristics including, but not limited to, race, age, baseline vital signs, and baseline glucocorticoid and mineralocorticoid replacement will also be summarized for each analysis population. For categorical variables, frequencies (n) and percentages (%) will be provided. Continuous variables will be summarized by number of non-missing observations (n), mean and/or median, standard deviation (SD) and/or percentiles, minimum (min), and maximum (max). If applicable, 90% confidence intervals will be calculated.

